### **Eligibility:**

Patients aged 18 years and older with isolated hip or femur fracture confirmed on x-ray.

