#### **Design:**

A randomized double-blind prospective superiority trial.

- Each patient will receive Morphine for analgesia prior to regional nerve block.
  - Patients < 65 years will receive Morphine 0.1 mg/kg every four hours as needed for 2 doses
  - Patients > 65 years will receive Morphine 0.05 mg/kg every four hours as needed for 2 doses
- **Treatment group:** will receive an ultrasound guided regional nerve block with Bupivacaine (0.5% or 5 mg/ml) 2.5 mg/kg (max dose 175 kg) + Ketamine (50 mg/ml) 2 mg/kg. Each patient will be given a volume of 40 mL - this will be a mixture of Bupivacaine, Ketamine and 0.9% NS to make up the full 40 ml.
- **Control group:** will receive an ultrasound guided regional nerve block with Bupivacaine 0.5% only. Each patient will be given a volume of 40 ml - this will be a mixture of Bupivacaine and 0.9% NS to make up the full volume of 40 mL
- The patients will be followed with respect to accrual time, follow up time, and total time of the block as well as a need for rescue analgesia as follows: every 15 minutes for the first hour; every 30 minutes for the next hour; every 1 hour for next 4 hours; every 4 hours for next 18 hours with end point of 24 hours or up until they are taken to surgery, whichever comes first.
- **Evaluation of the sensory blocks:** will be performed every 5 minutes after administration of the local anesthetic. The sensory block will be quantified as: 0 = Anesthesia (no sensation), 1 = Analgesia (decreased [dull] sensation), and 2 = no block (normal sensation), by using the pinprick test and comparing with the contralateral limb. The time elapsed from the injection to the onset of analgesia in the central sensory region of femoral nerve block will be taken as time of onset of the sensory block.
- **Rescue Analgesia:** If pain is not relieved and the participant requires rescue analgesia a weight-based dose of Morphine will be given at 0.1 mg/kg. In addition, an antidote (lipid emulsion) that will be given to patients who need it when they develop severe side effects.

**Data Collection:** Patient demographic, clinical and injury information, pain score, onset of motor and sensory block, rescue analgesia and side effects will be collected by using a data collection form by trained research assistant and associates.

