**Data Analysis:** Statistical Analyses will include frequency distributions, t-test and chi-square for comparison between and within the groups and Cox Linear Regression Analysis.  $P < .05$  will denote statistical significance. Statistical analyses will be conducted via SPSS version 24. [name] or equivalent will perform the statistical analyses.

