**Sample Size:**

A sample size of 110 patients (55 per group) will be needed to detect a 20 % difference in time to first rescue analgesia with  $\alpha = 0.05$  and SD of 2.5. We would recruit 120 patients (60 in each group) to account for any missing data and loss to follow-up.

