**Expected Outcomes:**

Primary Outcome: time to first rescue analgesia post-regional nerve blockade in each group

Secondary Outcomes:

- Change in pain score as measured by Visual Analog Scale: Patient to be approached at the following intervals: every 15 minutes for the first hour; every 30 minutes for the next hour; every 1 hour for next 4 hours; every 4 hours for next 18 hours with end point of 24 hours or up until they are taken to surgery, whichever comes first.

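### No baseline adjustment is fixed for time to first rescue analgesia, although fracture site, age and weight are known before the block; naming an adjusted Cox model is a cheap improvement

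*Combined protocol and SAP*

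**What the plan says.** The Expected Outcomes section gives "Primary Outcome: time to first rescue analgesia post-regional nerve blockade in each group". The Data Analysis paragraph is the whole analysis plan: "Statistical Analyses will include frequency distributions, t-test and chi-square for comparison between and within the groups and Cox Linear Regression Analysis". No method is assigned to the primary outcome, and no covariate is listed. The Design section calls the trial randomised and names no stratification factor.

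Three baseline facts are nevertheless needed before the block:

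- **Fracture site.** Eligibility requires "Patients aged 18 years and older with isolated hip or femur fracture confirmed on x-ray", so hip or femur is known from the x-ray.
- **Age.** The pre-block morphine dose per kg differs twofold either side of 65 years.
- **Body weight.** Doses are set per kg, and weight is also an exclusion criterion.

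The Data Collection paragraph records "Patient demographic, clinical and injury information" in general terms and does not itemise these variables.

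**The concern.** The trial mixes two injuries and takes adults of any age. In the treatment arm a per-kg bupivacaine dose is diluted to one fixed volume ("Each patient will be given a volume of 40 mL"), so concentration varies with body weight. Any of these could plausibly affect when pain returns. If they do, an analysis that ignores them uses less information than the trial holds. With 55 to 60 patients per arm and no stratification, a noticeable chance difference in one of them would also make an unadjusted result harder to defend. Leaving the model open adds a smaller problem: a t-test, a plain Cox model and any covariate set could all be called the planned analysis after the data are seen.

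**Working it through.** **1. The plan's own sample size.** Sample Size states "A sample size of 110 patients (55 per group) will be needed". The inputs it gives are a relative effect of 20% on the primary outcome, alpha 0.05 and SD 2.5. Power, sidedness, control mean and the unit of the SD are not given, so 55 per arm can be neither reproduced nor refuted. Solving backwards for a two-sided test at 80% power:

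- difference = 2.5 × (1.960 + 0.842) × √(2/55) = 1.336
- implied control mean = 1.336 / 0.20 = 6.68

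At 90% power the same steps give 1.545 and 7.73. A control mean of 6.75 h is used below as a value consistent with the 80% reading.

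**2. Dilution.** Treatment arm, 2.5 mg/kg in 40 mL: at 50 kg, 125 mg / 40 mL = 0.31%; at 70 kg, 175 mg / 40 mL = 0.44%. No per-kg amount is stated for the control arm, so this is shown for the treatment arm only. It makes weight a plausible covariate; it does not show that weight predicts the outcome.

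**3. Effect of adjustment in a Cox model (simulated).**

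From the documents: 55 per arm, 20% longer time, SD 2.5, censoring at surgery or 24 h.

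Assumed: hours as the unit, control mean 6.75 h, lognormal times, surgery uniform over 4 to 24 h, one binary factor present in 25% and one continuous covariate sharing R² (the fraction of log-time variance explained) equally, two-sided 5% Wald test. There were 2,000 replicates per setting and about 91 events per trial.

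| Assumed R² | Power unadjusted | Power adjusted (raw) | Size-corrected gain |
|---|---|---|---|
| 0.02 | 65% | 66% | about 0.5 points |
| 0.10 | 63% | 68% | about 2 points |
| 0.20 | 65% | 75% | about 6 points |
| 0.30 | 64% | 78% | about 10 points |

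The last column is smaller than the raw difference because, with no treatment effect, the adjusted Wald test rejects in about 6% to 8% of trials in this set-up instead of 5%. Lognormal times do not give proportional hazards, and part of the raw gain comes from that. The Monte Carlo standard error of one power figure is √(0.65 × 0.35 / 2000) = 0.011, so the 0.5-point gain at R² 0.02 cannot be told from zero.

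The hazard ratio moves from about 0.60 unadjusted to 0.58, 0.55 and 0.53 adjusted at R² 0.10, 0.20 and 0.30.

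**4. Linear cross-check.** For a comparison of means, residual SD = 2.5 × √(1 − R²). Starting from 80% power, this gives 80.8%, 84.0%, 87.9% and 91.8% at R² 0.02, 0.10, 0.20 and 0.30. The arithmetic does not transfer directly to a Cox model; it shows only the same pattern of small gains for weak covariates and larger gains for strong ones.

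**5. Chance imbalance.** For a factor present in 25% of patients:

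- SD of the between-arm difference = √(2 × 0.25 × 0.75 / 55) = 0.083
- P(difference of 10 percentage points or more) = 2 × [1 − Φ(0.10 / 0.083)] ≈ 0.23

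For a given continuous covariate, the standardised difference has SD √(2/55) = 0.19, and P(above 0.25 SD) ≈ 0.19.

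**The case against.** The strongest reply is that an unadjusted comparison in a randomised trial is valid, and that adjusting the primary analysis is a design preference. That stands, and it is why this is not called an error. Four stronger readings are tempting, and the documents support none of them.

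- **That the plan commits to an unadjusted primary analysis.** A reader might infer this from the t-test and chi-square. The same sentence lists a Cox regression, which can carry covariates. The model is unspecified, not unadjusted.
- **That the covariates are strong and power is being thrown away.** Nothing in the documents says how well fracture site, age or weight predict time to rescue. If they are weak, the gain is negligible.
- **That omitting them biases the hazard ratio towards 1.** The move from 0.60 to between 0.58 and 0.53 reflects non-collapsibility: the marginal and conditional hazard ratios are different quantities. Chance imbalance does not bias the unadjusted test or raise its type I error either.
- **That imbalance in fracture site is likely.** The figure is about 23%, at an assumed prevalence.

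A fair technical point also remains. A linear weight term may not follow the dilution effect if a dose maximum applies. The maximum in the Design section is printed as 175 kg, which cannot be read as a drug amount. That passage has to be reconciled before the form of the weight term is settled.

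**Conclusion.** The point holds as a free or cheap improvement. Neither the design nor the analysis fixes any baseline adjustment for the primary outcome, although three candidate covariates are known before treatment. The size-corrected gain is about 0.5 to 10 percentage points of power for R² from 0.02 to 0.30, with little lost if the covariates turn out weak. That range rests on the assumed R², the 6.75 h mean, the SD in hours, lognormal times, the surgery-time distribution and the 25% prevalence; the documents cannot show where in the range this trial lies. The firmer benefits are a result that is easier to read if the arms differ by chance, and a covariate set that cannot be chosen after the data are seen.

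**What to change.** Add to the Data Analysis paragraph:

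> The primary treatment effect is the hazard ratio from a Cox model with terms for arm, fracture site (hip vs femur), age and body weight, fixed before unblinding; the unadjusted result is shown as a sensitivity analysis.

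Confirm that the three variables are separate items on the data collection form. If enrolment has not started, stratifying the randomisation list by fracture site is an option.

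The cost is one sentence and no extra assessments. There are two downsides. The hazard ratio becomes a conditional effect and should be described as such. The adjusted Wald test can be slightly anti-conservative at about 90 events if hazards are not proportional. For that reason, keep to three covariates and report the unadjusted test alongside.

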**Sample Size:**

A sample size of 110 patients (55 per group) will be needed to detect a 20 % difference in time to first rescue analgesia with  $\alpha = 0.05$  and SD of 2.5. We would recruit 120 patients (60 in each group) to account for any missing data and loss to follow-up.

**Expected Outcomes:**

Primary Outcome: time to first rescue analgesia post-regional nerve blockade in each group

Secondary Outcomes:

- Change in pain score as measured by Visual Analog Scale: Patient to be approached at the following intervals: every 15 minutes for the first hour; every 30 minutes for the next hour; every 1 hour for next 4 hours; every 4 hours for next 18 hours with end point of 24 hours or up until they are taken to surgery, whichever comes first.
